1.4.3 Discussion

The nature of the target, the mechanism of action and safety profile of Atomoxetine are well known and understood.

In the context of the unmet medical need and anticipated benefit of development of the reliable test battery to measure impulsivity, the benefit risk evaluation of the compound, based upon the available clinical information, is favourable.

Considering the medical need for the development of a better tolerated and more effective treatments for psychiatric patients, the expected benefit outweighs the potential risks.

The impulsivity tool set developed in this trial could be implemented in the future trials for patients screening and to enable early decision making. Furthermore, these tests may enable to select the patients most suitable for inclusion in early patient clinical studies and could also be included as secondary endpoints in phase II-III clinical studies.

2. TRIAL OBJECTIVES AND ENDPOINTS

The overall goal of this study to establish appropriate protocols for impulsivity tasks.

2.1 MAIN OBJECTIVES, PRIMARY AND SECONDARY ENDPOINTS

2.1.1 Main objectives

The main objective of this trial is to identify the best-suited impulsivity measures for use in the future clinical trials, to investigate pharmacological modulation of impulsivity by atomoxetine after single dose and at steady-state, and to assess effect sizes and population variability.

[figure not shown]
- The primary objectives are to investigate the effect of atomoxetine on impulsivity after single dose and at steady state measured by the total score of BIS-11 and S-UPPS-P Impulsive Behavior Scale.
- The secondary objective is to evaluate the safety of atomoxetine.

2.1.2 Primary endpoint(s)

- Change from baseline in total score of Barratt Impulsiveness Questionnaire v.11 (BIS-11) after single dose (at day 1)
- Change from baseline in total score of Barratt Impulsiveness Questionnaire v.11 (BIS-11) at steady state (at day 14)
- Change from baseline in total score of S-UPPS-P Impulsive Behavior Scale after single dose (at day 1)
- Change from baseline in total score of S-UPPS-P Impulsive Behavior Scale at steady state (at day 14)

2.1.3 Secondary endpoint(s)

Percentage of patients with (S)AEs.

3. DESCRIPTION OF DESIGN AND TRIAL POPULATION

3.1 OVERALL TRIAL DESIGN

This is a multi-center, randomized, double-blind, placebo controlled parallel-group trial in patients with ADHD. A targeted total of approx. 96 patients with ADHD meeting the entry criteria are planned to be randomized into this trial.

Patients will be enrolled into the trial once consent has been signed. Patients suitable after screening will undergo base-line impulsivity assessments at Visit 2 and will be randomized to the 2-week double-blind treatment period (placebo or Atomoxetine in 1:1 ratio) at Visit 3. After the completion of the 2-week double-blind treatment period or following early discontinuation of trial medication at any point, patients will complete the last planned safety visit (End of Trial visit) 4 days after the last drug intake.

An overview of all relevant trial activities is provided in the [Flow Chart](#). For visit schedules and details of trial procedures at selected visits, refer to Sections [6.1](#) and [6.2](#), respectively.

3.2 DISCUSSION OF TRIAL DESIGN, INCLUDING THE CHOICE OF CONTROL GROUP(S)

This is an exploratory, randomized, double-blind, parallel arm, multiple dose, active comparator trial of Atomoxetine (impulsivity-reducing ADHD medication) and Placebo, with a 3 weeks screening period, 2-week treatment period and a 4-days follow-up, in patients with moderate ADHD.

Patients will be randomized according to a 1:1 ratio to either Atomoxetine or Placebo in a blinded fashion.

The effects on impulsivity in behavioral laboratory tasks will be collected and assessed at baseline, on day 1 after single dose, and day 14 at steady state in addition, safety measures will be collected until end of trial. Collectively, this information will help to establish appropriate protocols for impulsivity tasks and facilitate the design of the future clinical programs.

3.3 SELECTION OF TRIAL POPULATION

Impulsivity is a primary symptom of ADHD, therefore subjects with moderate symptoms of ADHD will be included in this trial.

The total of approximately 96 patients (80 evaluable patients with 40 patients per arm) are planned to be randomized into the study. It is planned that approximately 5 trial centers will be participating in this trial to ensure sufficient number of patients are randomized. It is expected that approximately 15-20 patients will be randomized at each trial center. If enrolment is delayed, additional sites may be recruited. To avoid differential cultural influence on study results, the study will be conducted in 1 country only. It is expected that a significant proportion of study participants, especially the younger ones, will not be regularly receiving any of the prohibited medication, prior to the onset of the trial. Investigators will be prompted to preferentially include patients who are not in receipt of regular pharmacological treatment for ADHD (thus require no discontinuation). Patients who are on treatment for ADHD should have successfully sustained medication-free periods in their medical history, without experiencing any significant deterioration based on medical records.

Screening of patients for this trial is competitive, i.e. screening for the trial will stop at all sites at the same time once a sufficient number of patients has been screened. Investigators will be notified about screening completion and will then not be allowed to screen additional patients for this trial. Patients already in screening at this time will be allowed to continue to randomisation if eligible.

A log of all patients enrolled into the trial (i.e. who have signed informed consent) will be maintained in the Investigator Site File (ISF) irrespective of whether they have been treated with investigational drug or not.

If retrospectively it is found that a patient has been randomized in error (=did not meet all inclusion criteria or met one or more exclusion criteria), the sponsor or delegate should be contacted immediately. Based on an individual benefit-risk assessment a decision will be made whether continued trial participation is possible or not.

3.3.1 Main diagnosis for trial entry

Patients with a stable clinical presentation must have moderate symptoms of ADHD with combined score of 4 or higher in Clinical Global Impression-ADHD-Severity (CGI-ADHD-S) and Hyperactivity/Impulsivity subscale min 8.

Please refer to section [8.3.1](#) (Source Documents) for the documentation requirements pertaining to the in- and exclusion criteria.

3.3.2 Inclusion criteria

1. Male and female subjects, 18-45 years of age at the time of consent meeting diagnostic criteria of ADHD per DSM-5 at screening visit and currently undergoing diagnostic assessment and/or treatment for ADHD
2. Signed and dated written informed consent in accordance with ICH-GCP and local legislation prior to admission to the trial.

Proprietary confidential information © 2024 Boehringer Ingelheim International GmbH or one or more of its affiliated companies

3. A diagnosis of the moderate symptoms of ADHD confirmed with combined score of 4 or higher in Clinical Global Impression-ADHD-Severity (CGI-ADHD-S) at Screening; Hyperactivity/Impulsivity subscale min 8 (at least moderate for impulsivity measure with ADHD checklist)
4. Able and willing to discontinue the use of any psychotropic medications for treatment of ADHD symptoms, as well as of all relevant co-medication for comorbid conditions during the study (for reference see section [4.2.2.1](#) and [Appendix 10.2](#))
5. Women of childbearing potential (WOCBP)¹ must be ready and able to use highly effective methods of birth control per ICH M3 (R2) that result in a low failure rate of less than 1% per year when used consistently and correctly. A list of contraception methods meeting these criteria and instructions on the duration of their use is provided in the patient information.

3.3.3 Exclusion criteria

1. Per DSM-5, had ever met diagnostic criteria for schizophrenia, schizoaffective disorder, schizophreniform disorder, bipolar disorder, delusional disorder or MDD with psychotic features at the time of screening.
2. Diagnosis of any mental disorder (according to DSM-5) that was primary focus of treatment within 6 months prior to Screening or at Baseline (as per clinical discretion of the investigator). *
3. Any psychiatric disorder, including the ones mentioned under #1, that in the opinion of the investigator would compromise participants' safety and/or validity of the data.
4. Current or recent (in the 6 months prior to screening) suicidal ideation or behaviour of type 4 or 5 in the C-SSRS.
5. Any finding in the medical examination (including BP, PR, temperature, or ECG) deviating from normal and assessed as clinically relevant by the investigator.
6. Repeated measurement of systolic blood pressure outside the range of 90 to 145 mmHg, diastolic blood pressure outside the range of 45 to 90 mmHg, or pulse rate outside the range of 45 to 95 bpm.
7. A marked baseline prolongation of QT/QTc interval (such as QTc intervals that are repeatedly greater than 450 ms in males or repeatedly greater than 470 ms in females) or any other relevant ECG finding at screening.
8. A history of additional risk factors for *Torsade de Pointes* (such as heart failure, hypokalaemia, or family history of Long QT Syndrome).
9. Any laboratory value outside the reference range that the investigator considers to be of clinical relevance.
10. Any evidence of a concomitant disease assessed as clinically relevant by the investigator (gastrointestinal, hepatic, renal, respiratory, cardiovascular, metabolic, immunological, or hormonal disorders).
11. Diseases of the central nervous system (including but not limited to any kind of seizures, stroke, brain tumor or any other major neurological or developmental illness).

Proprietary confidential information © 2024 Boehringer Ingelheim International GmbH or one or more of its affiliated companies

12. Major surgery (major according to the investigator's assessment) performed within 8 weeks prior to randomisation or planned within 2 months after screening.
13. Any documented active or suspected malignancy or history of malignancy within 5 years prior to screening, except appropriately treated basal cell carcinoma of the skin or in situ carcinoma of uterine cervix.
14. History of relevant orthostatic hypotension, fainting spells, or blackouts
15. History of relevant allergy or hypersensitivity (including allergy to the trial medication or its excipients) or known contraindications to atomoxetine.
16. Patients who must or wish to continue the intake of restricted medications (see section [4.2.2.1](#)) or any drug considered likely to interfere with the safe conduct of the trial.
17. Patients not expected to comply with the protocol requirements or not expected to complete the trial as scheduled (e.g. chronic alcohol or drug abuse or any other condition that, in the investigator's opinion, makes the patient an unreliable trial participant).
18. Known pharmacogenetic CYP2D6 status (poor metabolizers).
19. Drug abuse or positive drug screening.
20. Previous enrolment in this trial, or currently enrolled in another drug trial, or less than 30 days since ending another drug trial or receiving other investigational treatment(s).
21. Women who are pregnant, nursing, or who plan to become pregnant while in the trial.
22. History or evidence of narrow angle glaucoma.
23. History or evidence of pheochromocytoma.
24. Chronic or relevant acute infections.

1. A woman is considered of childbearing potential (WOCBP), i.e. fertile, following menarche and until becoming post-menopausal unless permanently sterile.

Permanent sterilisation methods include hysterectomy, bilateral salpingectomy and bilateral oophorectomy.

Tubal ligation is NOT a method of permanent sterilisation.

* The following are not excluded: Substance Induced Mood Disorder, Major Depressive Disorder in remission, Generalized Anxiety Disorder in remission, Post-Traumatic Stress Disorder in remission, recreational/occasional substance use as long as willing to stop for duration of the study, Borderline Personality Disorder.

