3.3.4.1 Discontinuation of trial treatment

Ideally, the patient should attend the End of Trial visit. Should the patient not agree, at least phone contact should occur at the scheduled visit time point to collect the most relevant information: vital status (please see section [5.2.6.2.1](#)), outcome events, adverse events, or last contact date in case of lost to follow-up.

An individual patient will discontinue trial treatment if:

- The patient wants to discontinue trial treatment. The patient will be asked to explain the reasons but has the right to refuse to answer.
- The patient has repeatedly shown to be non-compliant with important trial procedures and, in the opinion of the investigator, the safety of the patient cannot be guaranteed as he / she is not willing or able to adhere to the trial requirements in the future.
- The patient needs to take concomitant medication that interferes with the safety of the investigational medicinal product or other trial treatment (refer to sections [4.2.2.1](#)).
- The patient can no longer receive trial treatment for medical reasons such as surgery, adverse events, other diseases, or pregnancy. The patient shows disease progression/worsening that precludes further participation in the trial per investigator's clinical judgement. The participant develops suicidal ideation of type 4 or 5 in the C-SSRS (i.e., active suicidal thought with intent but without specific plan, active suicidal thought with plan and intent) or suicidal behavior (i.e. actual attempt, interrupted attempt, aborted attempt or preparatory acts or behavior). If new efficacy / safety information becomes available, Boehringer Ingelheim will review the benefit-risk-assessment and, if needed, discontinue the trial treatment for all patients or take any other appropriate action to guarantee the safety of the trial patients.

Even if the trial treatment is discontinued, the patients remain in the trial and, given their agreement, will undergo the procedures for early treatment discontinuation and follow-up as outlined in the [Flow Chart](#) and section [6.2.3](#).

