5.2.5 Other safety parameters

5.2.5.1 Assessment of suicidality

Suicidal risk will be assessed by the C-SSRS. The C-SSRS is a semi-structured, investigator rated interview, developed by clinical experts in cooperation with the FDA, assessing both suicidal behavior and suicidal ideation. It does not give a global score but provides some categorical and some severity information specifically for behavior and ideation. The C-SSRS is completed by the interviewer.

The C-SSRS has been widely used in large multi-national clinical trials. The C-SSRS will be administered first at screening (Visit 1) (using the 'Baseline / Screening' version) with the aim to exclude subjects with active moderate or severe symptomatology within a specified time prior to screening.

After screening (Visit 1) the assessment ‘since last visit’ will be performed on days 1, 4, 8, 10, 14 and EOT (‘Since Last Visit version’). The investigator is to review/consider the C-SSRS results for plausibility and clinical relevance. If the positive report is confirmed, appropriate actions for the subject’s safety have to be initiated.

All C-SSRS reports of suicidal ideation type 4 or 5 and all reports of suicidal behavior must be reported as separate SAEs by the investigator.

For ‘Self-injurious behavior, no suicidal intent’ (Type 11) standard AE / SAE reporting rules are to be applied.

For each C-SSRS report of suicidal ideation type 1, 2 or 3 after start of the trial, the investigator is to decide based on clinical judgment whether it represents an AE as defined in the protocol, and if it is considered an AE then it must be reported accordingly.

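### Exclusion criterion 4 ties suicidal behaviour to C-SSRS types 4 and 5, which this protocol uses only for ideation, so read literally it does not exclude recent suicidal behaviour by itself

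*Protocol*

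**What the plan says.** Exclusion criterion 4 in protocol section 3.3.3 reads "Current or recent (in the 6 months prior to screening) suicidal ideation or behaviour of type 4 or 5 in the C-SSRS".

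Two other sections set rules on the same scale:

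- **Section 3.3.4.1** requires treatment to stop if "The participant develops suicidal ideation of type 4 or 5 in the C-SSRS (i.e., active suicidal thought with intent but without specific plan", the alternative being active thought with both plan and intent. It then adds a second trigger: "or suicidal behavior (i.e. actual attempt, interrupted attempt, aborted attempt or preparatory acts or behavior".
- **Section 5.2.5.1** sets the reporting rule: "All C-SSRS reports of suicidal ideation type 4 or 5 and all reports of suicidal behavior must be reported as separate SAEs". It leaves the lower ideation types to clinical judgement ("For each C-SSRS report of suicidal ideation type 1, 2 or 3 after start of the trial"). For self-injury without suicidal intent it says "Type 11) standard AE / SAE reporting rules are to be applied".

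Section 5.2.5.1 also describes the Baseline/Screening version given at Visit 1 "with the aim to exclude subjects with active moderate or severe symptomatology within a specified time prior to screening". After Visit 1 the since-last-visit version is used; it "will be performed on days 1, 4, 8, 10, 14 and EOT".

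**The concern.** Criterion 4 has two nouns, ideation and behaviour, and one type restriction placed after both. If types 4 and 5 are grades of ideation, the restriction cannot be met by any behaviour, and the reference to behaviour excludes nobody.

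Section 1.4.2 lists suicide attempts and suicidal ideation among the events reported with atomoxetine and offers proactive screening as the mitigation. Criterion 4 is where the screening result becomes an eligibility decision. Section 1.4.1 states that participation brings no therapeutic benefit, and section 4.1.2 acknowledges that the first dose (80 mg) is above the usual 40 mg start. A patient with recent suicidal behaviour should not get past this criterion on a point of wording.

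What is at stake is the safety of an individual patient, and possibly different decisions at different sites.

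**Working it through.** No arithmetic applies. The check sets the protocol's uses of the C-SSRS type numbers side by side and then tests each way of reading criterion 4.

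**1. What the type numbers refer to**

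| Place | Types 1–3 | Types 4–5 | Suicidal behaviour |
|---|---|---|---|
| 3.3.3, criterion 4 | not mentioned | ideation or behaviour | same phrase, same restriction |
| 3.3.4.1, stopping rule | not mentioned | ideation: intent, without or with a plan | separate item, four categories, no number |
| 5.2.5.1, reporting | ideation | ideation | separate item, all reports, no number |

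Section 5.2.5.1 also numbers non-suicidal self-injury as type 11, above the ideation types. All five of types 1 to 5 are called ideation. Of the four behaviour categories in section 3.3.4.1 (actual, interrupted and aborted attempt; preparatory acts or behaviour), none is given type 4 or 5.

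**2. Possible readings of criterion 4**

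- (a) The restriction applies to both nouns, which is the ordinary reading. Type 4 or 5 ideation excludes; the behaviour part is empty.
- (b) The restriction applies to behaviour only. The behaviour part is still empty, and any ideation at all would exclude.
- (c) The restriction applies to ideation only. Type 4 or 5 ideation excludes, and so does any suicidal behaviour. This matches sections 3.3.4.1 and 5.2.5.1, but the restriction has to skip the noun next to it.

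Only (c) excludes behaviour in its own right.

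**3. Who falls through under (a)**

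A patient with type 4 or 5 ideation recorded in the 6 months is excluded whatever the behaviour. The gap is therefore limited to patients who had one of the four behaviours in that window and no type 4 or 5 ideation recorded in it.

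**4. Whether another rule catches them**

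| Provision | Why it does not close the gap by rule |
|---|---|
| Criterion 2 | Needs a mental disorder as primary focus of treatment, at the investigator's discretion; its footnote exempts borderline personality disorder and some disorders in remission |
| Criterion 3 | Investigator's opinion about a psychiatric disorder, not about the behaviour |
| Criterion 5, with section 6.2.1 (medical examination includes relevant history) | Investigator's judgement of clinical relevance |
| Criterion 17 | Concerns expected compliance and completion |
| Section 3.3.1 | Asks for a stable presentation, which is not defined |
| Section 5.2.5.1, screening aim | States an aim with an unspecified window; names no behaviour |

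Of the 24 exclusion criteria, only no. 4 names suicidality.

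**5. Whether later assessments catch them**

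The since-last-visit version on Day 1 is completed before the first dose (section 6.2.2), so behaviour arising after screening should be found. It does not ask again about the earlier 6 months. That history is judged once, at Visit 1, against criterion 4.

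**The case against.** The best defence is that a criterion should be read so that all its words have effect. Reading (c) does that, and it agrees with the stopping rule and the reporting rule. Anyone who knows the scale would see what was meant. The route to harm is also narrow: the investigator has just given the screening C-SSRS, must take the behaviour part as empty, and must then decline to use criteria 2, 3, 5 or 17. Criterion 5 matters here because it needs no psychiatric diagnosis and is outside the footnote to criterion 2. Dosing lasts 14 days with repeated C-SSRS assessments, and new behaviour stops treatment. Finally, the protocol does not print the full C-SSRS numbering, so the absence of a type 4 or 5 behaviour is an inference, and no misapplication at a site has been shown.

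Much of this stands. The intent is clear, the group is small, and many investigators would exclude such a patient on judgement. The numbering is inferred, but from two sections that agree with each other.

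It does not rescue the criterion. Section 8.3.1 requires source evidence that no exclusion criterion is met, and section 3.3 defines randomisation in error by reference to the written criteria. Under the ordinary reading, entering this patient would not count as an error under criterion 4. All the fallbacks depend on discretion or general wording. The result is also inconsistent: an attempt during the trial must end treatment, while one shortly before screening is not a written bar to entry.

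**Conclusion.** The concern holds. As worded, the only exclusion criterion that names suicidality does not exclude recent suicidal behaviour in its own right. It is most likely a drafting slip, not a decision to admit such patients, but it sits in an operative safety rule and should be fixed.

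The effect is limited to patients with suicidal behaviour and no recorded type 4 or 5 ideation in the 6 months before screening. The documents do not give the frequency of this group. I assume it is low among the at most 96 patients to be entered, on the view that many patients with a recent attempt would also have type 4 or 5 ideation recorded. That is a judgement, not a figure from the plan. Whether sites already apply the intended rule cannot be told from the documents. Primary endpoints, estimand and planned analyses are not affected.

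**What to change.** Replace criterion 4 with a rule in two parts, for example:

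*Suicidal ideation of C-SSRS type 4 or 5, or any suicidal behaviour (actual, interrupted or aborted attempt, or preparatory acts or behaviour), currently or within the 6 months before screening.*

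This keeps the present window and uses the behaviour categories already listed in section 3.3.4.1. Any site eligibility form should carry the same wording.

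The cost is one sentence in an amendment. No new assessment is needed, because the Baseline/Screening C-SSRS is already given at Visit 1. The downside is possibly a few more screen failures.
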